1. SYNOPSIS

Title of study: A Phase 2, Open-Label, Multiple-Dose Study to Evaluate the Safety, Tolerability, Pharmacokinetics, and Pharmacodynamics of NBI-74788 in Pediatric Subjects with Congenital Adrenal Hyperplasia

Study number: NBI-74788-CAH2008

Study center(s): Approximately 5 study centers in North America

Objectives:

- To assess the safety and tolerability of NBI-74788 in pediatric subjects 14 to 17 years of age with congenital adrenal hyperplasia (CAH).
- To evaluate the effect of repeated doses of NBI-74788 on endogenous levels of pharmacodynamic (PD) biomarkers in pediatric subjects with CAH.
- To evaluate the pharmacokinetics (PK) of NBI-74788 and metabolites in pediatric subjects with CAH.

Methodology: This is a Phase 2, open-label, multiple-dose study to assess the safety, tolerability, PK, and PD of NBI-74788 in approximately 12 pediatric female and male subjects (14 to 17 years of age) with a documented medical diagnosis of classic 21-hydroxylase deficiency CAH. NBI-74788 50 mg twice daily (bid) will be administered for 14 consecutive days with breakfast and evening meals beginning on the evening of Day 1.

Parental or legal guardian informed consent with signed and witnessed study subject assent will be obtained prior to any study-related procedures. Subjects will then be screened for up to approximately 3 weeks (Days -28 to -8) for eligibility to participate in the study. During screening, subjects will provide a blood sample in the morning between 0700 and 1000 hours (prior to first morning dose of hydrocortisone) to determine their 17-hydroxyprogesterone (17-OHP) levels for study entry.

Eligible subjects who have a screening 17-OHP level ≥800 ng/dL will be admitted to the study center on Day -7 for 1 night and have baseline serial PD samples collected over a 24-hour period beginning that evening. Baseline serial PD samples will be collected at approximately 1845, 2000, 2300, 0100, 0300, 0700, 1000, 1500, and 1900 hours.

The subjects' usual morning dose of steroidal treatments will be administered after the 1000 hours PD sample is collected on Day -6. Subjects will be discharged on Day -6 after the last PD sample is collected.

Subjects will be admitted to the study center on Days 1 and 14 (first and last day of dosing). Subjects will have a blood sample collected on Day 1 for the first dose of study drug. The first dose of study drug, NBI-74788 50 mg, will be administered at approximately 1900 hours with subjects' evening meal on Day 1. Study drug will be administered at the study center on Days 2 and 14 with subjects' breakfast and evening meals, respectively. The subjects' usual morning dose of concurrent steroidal treatments, study drug dosing, and breakfast (snacks will be allowed prior to breakfast) will be delayed until after the 15-hour postdose PD samples are collected (ie, at approximately 1000 hours) on Day 2. The subjects' usual morning dose of concurrent steroidal treatments will be administered after the 15-hour postdose PD samples are collected (ie, at approximately 1000 hours) on Day 15. Subjects will be discharged from the study center in the evening on Days 2 and 15 following completion of all study-related procedures for those days. Study drug will be self-administered at home under parent/guardian supervision at approximately 0700 hours (with breakfast) and 1900 hours (with evening meal) on Days 3 to 13.

On Day 7 during the treatment period, PK, PD, and safety assessments will be conducted in an outpatient setting at the study center.

Follow-up visits on Days 17 and 21 will be conducted at the study center or by a qualified home healthcare provider at the subject's home (based on the subject's preference). A final study visit will be conducted at the study center approximately 3 weeks after the last dose of study drug (on Day 35 or early termination). There will be a visit window of -8 hours for Day 7, -8 hours/+3 days for Days 17 and 21, and +7 days for the final study visit (Day 35 or early termination). Safety, tolerability, PK, and PD will be assessed at scheduled times throughout the study.

Study Population: Approximately 12 pediatric female and male subjects (14 to 17 years of age) with a documented medical diagnosis of classic 21-hydroxylase deficiency CAH, who meet all protocol eligibility criteria, will be enrolled.

Duration of treatment: The expected duration of study participation for each subject is approximately 9 weeks, including up to approximately 3 weeks for screening, a 24-hour PD baseline period (approximately 7 days prior to the first day of dosing), 14 days of dosing, and a follow-up period of approximately 3 weeks.

Test product, dose, and mode of administration: NBI-74788 will be supplied as capsules containing 50 mg of NBI-74788 for oral administration. One capsule of study drug will be administered orally at approximately 0700 hours with breakfast and at approximately 1900 hours with evening meal.

Reference therapy, dose, and mode of administration: Not applicable.

Criteria for evaluation

Pharmacokinetics:

Blood samples for PK analysis will be collected at the following times:

- Days 1 and 14: 15 minutes pre-evening dose and at 1, 4, and 6 hours post-evening dose (±5 minute window).
- Days 2 and 15: 8, 12, and 24 hours post-evening dose (±15 minute window; 24-hour post-evening dose blood sample on Day 15 only).
- Day 7: 12 hours (±2 hour window) after the Day 6 evening dose, prior to the Day 7 morning dose.
- Days 17 and 21: 72 hours (-8 hours/+3 days) and 168 hours (-8 hours/+3 days) post-final dose.
- Final study visit (+7 days; Day 35 or early termination).

The following plasma PK parameters will be calculated for NBI-74788 and metabolites for the Day 1 to 2 and the Day 14 to 15 sampling intervals:

- Area under the plasma concentration versus time curve from 0 to 12 hours (AUC₀₋₁₂).
- Observed maximum plasma concentration (C_{max}).
- Time to C_{max} (t_{max}).

Additional PK parameters for Days 14 to 15 only:

- Average plasma concentration at steady state (C_{avg}).
- Percent fluctuation at steady state (%fluctuation).
- Accumulation ratio at steady state.
- Apparent terminal half-life (t½).
- Apparent terminal rate constant (λz).
- Apparent mean residence time (MRT).
- Apparent systemic clearance after oral administration (CL/F) (NBI-74788 only).

Pharmacodynamics:

Blood samples for PD parameters will be collected at the following times:

• Screening (must be collected prior to first morning dose of hydrocortisone).

- Day -7 to Day -6 (24-hour PD baseline): at approximately 1845, 2000, 2300, 0100, 0300, 0700, 1000, 1500, and 1900 hours.
- Days 1 and 14: 15 minutes pre-evening dose and at 1, 4, and 6 hours post-evening dose (±5 minute window).
- Days 2 and 15: 8, 12, 15, 20, and 24 hours post-evening dose (± 15 minute window).
- Day 7: 12 hours (±2 hour window) after the Day 6 evening dose and prior to the Day 7 morning dose.
- Day 21: 168 hours (-8 hours/+3 days) following last dose.

Morning 17-OHP (serum; ng/dL) from the 8- and 12-hour postdose samples (collected at 0300 and 0700 hours).

17-OHP at all other times, androstenedione (serum; ng/dL), testosterone (serum; ng/dL), cortisol (serum; μ g/dL), and adrenocorticotropic hormone (ACTH; plasma; pg/mL).

Safety: Safety and tolerability will be monitored throughout the study and will include the following assessments:

- Treatment-emergent adverse events.
- Clinical laboratory tests (clinical chemistry, hematology, and urinalysis).
- Vital signs.
- Physical examinations (including musculoskeletal exam).
- 12-lead electrocardiograms (ECGs).
- Columbia-Suicide Severity Rating Scale (C-SSRS), Children's Version
- Brief Psychiatric Rating Scale for Children (BPRS-C).

Statistical methods: Safety, PK, and PD data will be summarized using descriptive statistics. Summaries of safety measures will include both observed values and changes from baseline. Summaries of PD measures will include both observed values and changes from timepoint-matched PD baseline values.

TABLE OF CONTENTS

| 1. | SYNOPSIS | 5 |
|--------|--|----|
| TABLE | OF CONTENTS | 8 |
| LIST O | F TABLES | 11 |
| LIST O | F FIGURES | 11 |
| 2. | LIST OF ABBREVIATIONS AND DEFINITIONS OF TERMS | 12 |
| 3. | ETHICS | 14 |
| 4. | INTRODUCTION | 14 |
| 4.1. | Background | 14 |
| 4.2. | NBI-74788 | 15 |
| 4.3. | Study and Dose Rationale | 17 |
| 5. | OBJECTIVES | 17 |
| 6. | STUDY DESIGN | 17 |
| 7. | STUDY POPULATION | 21 |
| 7.1. | Subject Inclusion Criteria | 21 |
| 7.2. | Subject Exclusion Criteria | 22 |
| 7.3. | Subject Identification and Replacement | 24 |
| 7.4. | Randomization | 24 |
| 8. | STUDY EVALUATIONS | 24 |
| 8.1. | Schedule of Assessments | 24 |
| 8.2. | Screening and Baseline Assessments | 27 |
| 8.2.1. | Serum 17-Hydroxyprogesterone | 27 |
| 8.2.2. | | 27 |
| 8.3. | Pharmacokinetic Assessments | 27 |
| 8.4. | Pharmacodynamic Assessments: Pharmacodynamic Biomarkers | 28 |
| 8.5. | Safety Assessments | 28 |
| 8.5.1. | Vital Sign Measurements | 28 |
| 8.5.2. | Medical History and Physical Examination | 29 |
| 8.5.3. | 12-Lead Electrocardiogram | 29 |
| 8.5.4. | Clinical Laboratory Assessments | 30 |
| 8.5.5. | Brief Psychiatric Rating Scale for Children | 31 |
| 8.5.6. | Columbia-Suicide Severity Rating Scale Children's Versions | 31 |

Neurocrine Biosciences, Inc., Study No. NBI-74788-CAH2008 Clinical Protocol Final Version

| 8.5.7. | Estimated Total Blood Sample Volume Required by Study | 31 |
|----------|---|----|
| 8.6. | Subject Study Diary | 32 |
| 8.7. | Specific Study Period Information | 32 |

2. LIST OF ABBREVIATIONS AND DEFINITIONS OF TERMS

17-OHP 17-hydroxyprogesterone

ACTH adrenocorticotropic hormone

AE adverse event

ALT alanine aminotransferase

AST aspartate aminotransferase

AUC area under the plasma concentration versus time curve

β-hCG β-human chorionic gonadotropin

bid twice daily

BPRS-C Brief Psychiatric Rating Scale for Children

CAH congenital adrenal hyperplasia
CFR Code of Federal Regulations

CK creatine kinase

C_{max} observed maximum plasma concentration

CRF1 corticotropin releasing factor 1

C-SSRS Columbia-Suicide Severity Rating Scale

DSM Diagnostic and Statistical Manual of Mental Disorders

DSPV Drug Safety and Pharmacovigilance

ECG electrocardiogram

eCRF electronic case report form
EDC electronic data capture

FDA Food and Drug Administration

GCP Good Clinical Practice

GGT gamma-glutamyl transferase HbsAg hepatitis B surface antigen

HCV-Ab hepatitis C antibody

HIV-Ab human immunodeficiency virus antibody

ICF informed consent form

ICH International Conference on Harmonisation of Technical Requirements for

Registration of Pharmaceuticals for Human Use

IRB institutional review board

Neurocrine Biosciences, Inc., Study No. NBI-74788-CAH2008 Clinical Protocol Final Version

MedDRA Medical Dictionary for Regulatory Activities

NBI Neurocrine Biosciences, Inc.

NOAEL no observed adverse effect level

PD pharmacodynamics

P-gp P-glycoprotein
PK pharmacokinetics

QTcF QT interval corrected for heart rate using Fridericia's correction

SAE serious adverse event SAP statistical analysis plan

t_{1/2} apparent terminal half-life

TEAE treatment-emergent adverse event

t_{max} time to reach observed maximum plasma concentration

ULN upper limit of normal

US United States
WBC white blood cell

3. ETHICS

The study will be conducted in accordance with Neurocrine Biosciences, Inc. (NBI) standards that meet regulations relating to Good Clinical Practice (GCP). These standards respect the following guidelines:

- GCP: Consolidated Guideline (International Conference on Harmonisation of Technical Requirements for Registration of Pharmaceuticals for Human Use [ICH; current version]).
- United States (US) Code of Federal Regulations (CFR) dealing with clinical studies (21 CFR parts 50, 54, 56, 312, and 314).
- Canada Food and Drugs Act and Regulations Part C, Division 5: Drugs for Clinical Trials Involving Human Subjects.
- Guidance for Clinical Trial Sponsors: Clinical Trial Applications, Effective March 2016, Health Canada Therapeutic Products Directorate, Health Products and Food Branch.

The ethical requirements of Institutional Review Boards (IRBs)/Ethics Committees and the informed consent forms (ICFs) are discussed in Section 13.

4. INTRODUCTION

4.1. Background

NBI-74788 is a selective corticotropin releasing factor 1 (CRF1) receptor antagonist that is being developed by NBI as a novel oral treatment for classic congenital adrenal hyperplasia (CAH) due to 21-hydroxylase deficiency, a condition that results in little or no cortisol biosynthesis. One clinical manifestation of the absence of cortisol is the lack of feedback inhibition of pituitary adrenocorticotropic hormone (ACTH) secretion. Increased ACTH levels cause adrenal hyperplasia and the enzyme mutation causes a shunting of cortisol precursor steroids to alternate pathways. Most notably, the shunting of androgens leads to virilization and other developmental complications in females and the over-accumulation of ACTH is associated with the formation of testicular adrenal rest tumors in males. In addition, since the same enzyme (21-hydroxylase) is used in the pathway for the biosynthesis of the mineralocorticoids, a number of these patients suffer from aldosterone deficiency which can result in dehydration and death due to salt-wasting. The prevalence of classic 21-hydroxylase deficiency CAH in the US general population, based on newborn screening, has been documented as 1:10,000 to 1:20,800 (Trakakis et al., 2010; Hertzberg et al., 2011), a figure that supports orphan drug designation.

Pediatric patients from birth through adolescence, and females in particular, appear to be the most vulnerable population of CAH sufferers and represent the subgroup of patients with the greatest unmet medical need (Cheng and Speiser, 2012; Merke and Poppas, 2013). Excessive androgen production in these younger patients results in early onset puberty and adrenarche, changes in skeletal maturation patterns, short stature caused by premature growth plate fusion, as well as significant hirsutism and acne problems. While survival is properly ensured through steroid replacement strategies based on physiologic dosing of glucocorticoids (eg, hydrocortisone) and mineralocorticoids (eg, fludrocortisone), these doses are often inadequate to suppress the accumulating ACTH and overproduction of progestogens and

[figure not shown]
10 May 2019 Confidential 14

androgens (eg, 17-hydroxyprogesterone [17-OHP], androstenedione, and testosterone). The uncontrolled symptoms of androgen excess, indeed, have a substantial impact on the day-to-day functioning and development of these patients. The glucocorticoid doses required to treat the androgen excess are typically well above the normal physiologic dose used for cortisol replacement alone (as in patients with Addison's disease). This increased exposure to glucocorticoids can lead to iatrogenic Cushing's syndrome, increased cardiovascular risk factors, glucose intolerance, reduced growth velocity, and decreased bone mineral density in CAH patients (Elnecave et al., 2008; King et al., 2006; Migeon and Wisniewski, 2001).

Corticotropin releasing factor is a hypothalamic hormone released directly into the hypophyseal portal vasculature and acts on specific CRF1 receptors on corticotropes in the anterior pituitary to stimulate the release of ACTH. Blockade of these receptors has been shown to decrease the release of ACTH in both animals and humans. Therefore, compounds that block CRF1 receptors have the potential to directly inhibit the excessive ACTH release that occurs in CAH and thereby allow for normalization of androgen production while using lower, more physiologic doses of hydrocortisone. The novel CRF1 receptor antagonist, NBI-74788, may provide an important therapeutic approach to treat patients with CAH.

4.2. NBI-74788

4.3. Study and Dose Rationale

The present Phase 2 study is designed to evaluate the safety, tolerability, pharmacokinetics (PK), and pharmacodynamics (PD) of NBI-74788 in pediatric subjects 14 to 17 years of age with classic CAH following multiple days of dosing twice daily 50 mg.

5. OBJECTIVES

The objectives of the study are as follows:

- To assess the safety and tolerability of NBI-74788 in pediatric subjects 14 to 17 years of age with CAH.
- To evaluate the effect of repeated doses of NBI-74788 on endogenous levels of PD biomarkers in pediatric subjects with CAH.
- To evaluate the PK of NBI-74788 and metabolites in pediatric subjects with CAH.

6. STUDY DESIGN

This is a Phase 2, open-label, multiple-dose study to assess the safety, tolerability, PK, and PD of NBI-74788 in approximately 12 pediatric female and male subjects (14 to 17 years of age) with a documented medical diagnosis of classic 21-hydroxylase deficiency CAH. NBI-74788 50 mg bid will be administered for 14 consecutive days with breakfast and evening meals beginning on the evening of Day 1.

Parental or legal guardian informed consent with signed and witnessed study subject assent will be obtained prior to any study-related procedures. Subjects will then be screened for up to approximately 3 weeks (Days -28 to -8) for eligibility to participate in the study. During

screening, subjects will provide a blood sample in the morning between 0700 and 1000 hours (prior to first morning dose of hydrocortisone) to determine their 17-OHP levels for study entry.

Eligible subjects who have a screening 17-OHP level ≥800 ng/dL will be admitted to the study center on Day -7 for 1 night and have baseline serial PD samples collected over a 24-hour period beginning that evening. Baseline serial PD samples will be collected at approximately 1845, 2000, 2300, 0100, 0300, 0700, 1000, 1500, and 1900 hours.

The subjects' usual morning dose of steroidal treatments will be administered after the 1000 hours PD sample is collected on Day -6. Subjects will be discharged on Day -6 after the last PD sample is collected.

Subjects will be admitted to the study center on Days 1 and 14 (first and last day of dosing). Subjects will have a blood sample collected on Day 1 for assessments will be collected on Day 1 prior to the first dose of study drug. The first dose of study drug, NBI-74788 50 mg, will be administered at approximately 1900 hours with subjects' evening meal on Day 1. Study drug will be administered at the study center on Days 2 and 14 with subjects' breakfast and evening meals, respectively. The subjects' usual morning dose of concurrent steroidal treatments, study drug dosing, and breakfast (snacks will be allowed prior to breakfast) will be delayed until after the 15-hour postdose PD samples are collected (ie, at approximately 1000 hours) on Day 2. The subjects' usual morning dose of concurrent steroidal treatments will be administered after the 15-hour postdose PD samples are collected (ie, at approximately 1000 hours) on Day 15. Subjects will be discharged from the study center in the evening on Days 2 and 15 following completion of all study-related procedures for those days. Study drug will be self-administered at home under parent/guardian supervision at approximately 0700 hours (with breakfast) and 1900 hours (with evening meal) on Days 3 to 13.

On Day 7 during the treatment period, PK, PD, and safety assessments will be conducted in an outpatient setting at the study center.

Follow-up visits on Days 17 and 21 will be conducted at the study center or by a qualified home healthcare provider at the subject's home (based on the subject's preference). A final study visit will be conducted at the study center approximately 3 weeks after the last dose of study drug (on Day 35 or early termination). There will be a visit window of -8 hours for Day 7, -8 hours/+3 days for Days 17 and 21, and +7 days for the final study visit (Day 35 or early termination). Safety, tolerability, PK, and PD will be assessed at scheduled times throughout the study.

The study design schematic is shown in Figure 1. A schematic of study drug dosing and blood draw timepoints is shown in Table 1.

Figure 1: Study Design Schematic

| | Screening | PD Baseline | 14-Day Dosing Period | | Follow-Period | | Final Study Visit/ET | | |
|-----|-----------|-------------|----------------------|--------------------------|---------------|-------|-------------------------|-----|----|
| | | | | | | | | | • |
| | | | | NBI-74788 (50 mg bid) | | | | | |
| | ı | 1 | ı ı | ı | 1 | 1 1 | ı | | 1 |
| | | | | | | | | | |
| Day | -28 to -8 | -7 to -6 | 2 | 7 | 14 1 | 15 17 | 21 | 1 3 | 35 |

bid=twice daily; ET=early termination; PD=pharmacodynamic.

Table 1: Study Drug Dosing and Blood Draw Timepoints Schematic

| Screening | PD Baseline (Day -7) | PD Baseline (Day -6) | Day 1 | Day 2 | Day 3 - Day 6 | Day 7 | Day 8 - Day 13 | Day 14 | Day 15 | Day 17 | Day 21 | Day 35 |
|--|----------------------------------|----------------------------------|-----------------------------|---|---------------|-------------------|----------------------|------------------------------|--|----------------------|--------------------------|----------------------------|
| | | PD: 0100, 0300, 0700 hr | | PK/PD: 8, 12 hr post | | PK/PD: Predose | | | PK/PD: 8, 12 hr post | | | |
| AM DOSIN | G | | | 1000 hr Delayed Dosing with Meal | 0700 hr | 0700 hr | 0700 hr | 0700 hr | | | | |
| PD/Labs: 0700 – 1000 hr (+ & & Serology) | | PD: 1000, 1500, 1900 hr | PK/PD/Labs: Predose + | PD: 15, 20, 24 hr post | | | | PK/PD: Predose | PD: 15, 20 hr post PK/PD/Labs: 24 hr post | PK: 72 hr post | PK/PD: 168 hr post | PK/Labs: 504 hr post |
| PM DOSIN | G | | 1900 hr | 1900 hr | 1900 hr | 1900 hr | 1900 hr | 1900 hr | | | | |
| | PD: 1845, 2000, 2300 hr | | PK/PD: 1, 4, 6 hr post | | | | | PK/PD: 1, 4, 6 hr post | | | | |

PD=pharmacodynamic; PK=pharmacokinetic.

Note: blood draws (pre- and post-dose) are relative to evening dosing.

7. STUDY POPULATION

This study will be conducted in approximately 12 pediatric female and male subjects (14 to 17 years of age) with a documented medical diagnosis of classic 21-hydroxylase deficiency CAH. Subjects must meet all inclusion criteria and no exclusion criteria in order to be enrolled.

7.1. Subject Inclusion Criteria

To participate in this study, subjects must meet the following criteria:

- 1. Have documentation of informed consent by the subject's parent(s) or legal guardian, and of assent by the study subject.
- 2. Be female or male between 14 to 17 years of age (inclusive).
- 3. Have a body weight (in kg) greater than or equal to the 10th percentile of his/her age- and gender-matched weight percentile at screening.
- 4. Be in good general health, as determined by medical history, physical examination, clinical laboratory assessments, and 12-lead ECG.
- 5. Have a medically confirmed diagnosis of classic 21-hydroxylase deficiency CAH that includes a serum 17-OHP level of ≥800 ng/dL at screening. A medically confirmed diagnosis will be satisfied if the subject is able to provide a medical record of the CAH diagnosis or the investigator can confirm the CAH diagnosis.
- 6. Have a serum cortisol concentration <5 μ g/dL and plasma ACTH concentration \geq 20 μ g/mL at screening, consistent with the classic 21-hydroxylase deficiency CAH diagnosis.

| 7. | Be on a stable regimen of steroidal | treatment for CAH | | |
|----|-------------------------------------|-------------------|---------------|----------------|
| | | | | |
| | | | that is expec | cted to remain |
| | stable throughout the study. | | | |
| | | | | |
| | | | | |

8. Subjects of childbearing potential must agree to use contraception consistently from screening until 30 days (females) or 90 days (males) after the last dose of study drug. A female subject of childbearing potential is defined as a female capable of becoming pregnant, which includes subjects who have had their first menstrual cycle (ie, menarche) and are not surgically sterile (ie, bilateral oophorectomy, hysterectomy or bilateral tubal ligation for at least 3 months prior to screening). A male subject of childbearing potential is defined as a subject who has reached spermarche and has not been vasectomized for at least 3 months prior to screening.

10 May 2019 Confidential 21

- 9. Female subjects of childbearing potential must have a negative serum β-human chorionic gonadotropin (β-hCG) pregnancy test at screening and negative urine pregnancy test at Day 1 (baseline).
- 10. Subjects must have a negative urine drug screen (negative for amphetamines, barbiturates, benzodiazepine, phencyclidine, cocaine, opiates, or cannabinoids) and negative alcohol breath test at screening, at the start of the 24-hour PD baseline period (Day -7), and on Day 1 (Day -7 and Day 1 eligibility based on urine drug screen and alcohol breath test conducted at the site). Subjects with a positive urine drug screen due to a stable medication regimen to treat a medical condition may participate in the study.
- 11. Be willing and able to adhere to the study regimen and study procedures described in the protocol and informed consent/assent forms, including all requirements at the study center and return for the follow-up visits.

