8.4. Pharmacodynamic Assessments: Pharmacodynamic Biomarkers

Approximately 7 mL of blood will be collected for each sample. PD biomarker samples will be sent to a central laboratory which will provide instructions and supplies to the study staff before study initiation.

Blood samples to measure cortisol (serum; $\mu g/dL$), 17-OHP (serum; ng/dL), androstenedione (serum; ng/dL), testosterone (serum; ng/dL), and ACTH (plasma; pg/mL) will be collected at:

- Screening (between 0700 and 100 hours; must be collected prior to first morning dose of hydrocortisone).
- Day -7 to Day -6 (24-hour PD baseline): at approximately 1845, 2000, 2300, 0100, 0300, 0700, 1000, 1500, and 1900 hours.
- Days 1 and 14: 15 minutes pre-evening dose and at 1, 4, and 6 hours post-evening dose (±5 minute window).
- Days 2 and 15: 8, 12, 15, 20, and 24 hours post-evening dose (± 15 minute window).
- Day 7: 12 hours (±2 hour window) after the Day 6 evening dose and prior to the Day 7 morning dose (study drug dosing should not occur until after the blood sample has been collected).
- Day 21: 168 hours (-8 hours/+3 days) following last dose.

The exact time of sampling in hour and minutes will be recorded.

The blood samples will be processed and stored as specified in the laboratory manual. These samples will be shipped on dry ice to the central laboratory for analysis. Refer to the laboratory manual for additional details.

An in-home service (phlebotomist) will be available for blood draws on Day 21.

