12.2. Sample Size

The sample size for this study is based on practical clinical considerations with no formal statistical power calculations.

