4.3. Clinical Assessments

Pharmacodynamic assessments include:

- Morning 17-OHP (serum; ng/dL) from the 12- and 15-hour postdose samples (collected at 0700 and 1000 hours).
- 17-OHP at all other times, androstenedione (serum; ng/dL), testosterone (serum; ng/dL), cortisol (serum; μg/dL), and adrenocorticotropic hormone (ACTH; plasma; pg/mL).

Pharmacokinetic assessments include:

The following plasma PK parameters will be calculated for crinecerfont and metabolites for the Day 1 to 2 and the Day 14 to 15 sampling intervals:

- Area under the plasma concentration versus time curve from 0 to 12 hours (AUC $_{0-12}$).
- Observed maximum plasma concentration (C_{max}).
- Time to C_{max} (t_{max}).

Additional PK parameters for Days 14 to 15 only:

- Average plasma concentration at steady state (C_{avg}).
- Percent fluctuation at steady state (%fluctuation).
- Accumulation ratio at steady state.
- Apparent terminal half-life ($t\frac{1}{2}$).
- Apparent terminal rate constant (λz) .
- Apparent mean residence time (MRT).
- Apparent systemic clearance after oral administration (CL/F) (crinecerfont only).

Safety assessments include:

- Adverse events (AEs).
- Clinical laboratory tests (clinical chemistry, hematology, and urinalysis).
- Vital signs.
- Physical examinations (including musculoskeletal exam).
- 12-lead electrocardiograms (ECGs).
- Columbia-Suicide Severity Rating Scale (C-SSRS), Children's Version

• Brief Psychiatric Rating Scale for Children (BPRS-C).

See Table 2 of the study protocol for a complete schedule of assessments.

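### Inclusion criterion 6 appears to give the ACTH entry threshold in μg/mL, while every place that states an ACTH reporting unit uses pg/mL: a million-fold mismatch, to be confirmed in the source PDF

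*Protocol*

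**What the plan says.** Criterion 6 in Protocol 7.1 pairs an upper limit on serum cortisol (below 5 μg/dL) with a lower limit on "plasma ACTH concentration". The ACTH part reads, in the text as extracted, "plasma ACTH concentration \geq 20 μ g/mL at screening".

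The criterion is binding. Protocol 7 states: "Subjects must meet all inclusion criteria and no exclusion criteria in order to be enrolled".

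The unit in which ACTH is measured appears in four other places, and in each it is pg/mL:

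- the pharmacodynamics part of the protocol synopsis;
- Protocol 8.4, "and ACTH (plasma; pg/mL) will be collected at" a list of times whose first entry is the screening visit;
- Protocol 12.7;
- SAP 4.3, "adrenocorticotropic hormone (ACTH; plasma; pg/mL".

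Other places, such as the footnotes to protocol Table 2 and SAP 9 and 9.2, name ACTH without a unit. Protocol 8.2.1 says that the screening draw measures 17-OHP and the other PD analytes in order to decide eligibility.

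**The concern.** An eligibility rule works by comparing a laboratory result with a threshold. Here the result would come back in pg/mL and the threshold is stated in μg/mL. A site cannot apply the criterion without either converting the threshold, which gives an eight-digit number in the reporting unit, or deciding for itself that a different unit was meant. Protocol 13.3 tells sites to follow the instructions exactly and requires a formal amendment for any change, so reinterpretation by the site is not an option that the protocol offers.

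What is at stake is the definition of who may enter the trial, and whether departures from criterion 6 can be judged. SAP 8.2 has a sponsor committee decide before database lock which major protocol deviations are important. That committee needs a settled unit before it can say whether a given ACTH value met the criterion.

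**Working it through.** The plan does not derive the threshold, so there is no figure of its own to reproduce. The check is a unit conversion and a comparison of the places where a unit is given.

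**Inputs**

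| Quantity | Value | Source |
|---|---|---|
| ACTH entry threshold, as extracted | at least 20 μg/mL | Protocol 7.1, criterion 6 |
| ACTH reporting unit | pg/mL | Protocol synopsis, 8.4, 12.7; SAP 4.3 |
| Cortisol entry threshold | below 5 μg/dL | Protocol 7.1, criterion 6 |
| 17-OHP entry threshold | "serum 17-OHP level of ≥800 ng/dL at screening" | Protocol 7.1, criterion 5 |

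**Step 1: size of the mismatch.** 1 μg = 1,000,000 pg, so 20 μg/mL = 20 × 1,000,000 = 20,000,000 pg/mL. Against the same number in the reporting unit, 20,000,000 / 20 = 1,000,000.

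**Step 2: is it the same measurement?** Yes. Protocol 8.4 includes the screening sample among those for which ACTH is in pg/mL, and Protocol 8.2.1 uses that draw for eligibility. The two units therefore apply to one result.

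**Step 3: can the other entry thresholds show which unit was meant?** Put all three on one scale (1 dL = 100 mL):

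- cortisol: 5 μg/dL / 100 = 0.05 μg/mL = 50,000 pg/mL;
- 17-OHP: 800 ng/dL / 100 = 8 ng/mL = 0.008 μg/mL = 8,000 pg/mL.

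Read as μg/mL, the ACTH threshold is 20 / 0.05 = 400 times the cortisol cut-off and 20 / 0.008 = 2,500 times the 17-OHP cut-off. Read as pg/mL, it is 50,000 / 20 = 2,500 times below the cortisol cut-off and 8,000 / 20 = 400 times below the 17-OHP cut-off. The comparison shows how far apart the two readings lie, but it is symmetric and does not choose between them. The point therefore rests on the conflict of units in Steps 1 and 2.

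**Step 4: could the μ be a misread p?** The protocol synopsis and Protocol 12.7 give cortisol with the same spaced μ g and then ACTH as pg/mL in the same sentence. Protocol 8.4 has formula residue in the cortisol unit and still shows pg/mL for ACTH. So in three comparable lines the two prefixes were kept apart. In criterion 6 the denominators differ (dL for cortisol, mL for ACTH), so the cortisol unit was not simply repeated whole. This argues against assuming a reading error but does not exclude one.

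**The case against.** The strongest objection is that the protocol itself may be correct. The criterion 6 line carries conversion residue: a formula code in place of the inequality sign, and a detached μ. Criterion 5, just above it, shows a clean sign and unit. The reading of this PDF also goes wrong elsewhere: QTcF appears as OTcF in Protocol 8.10.1, and in Table 2 the PD sampling row is repeated with a lost P and Greek letters in place of the Xs. The lines that show pg/mL correctly are running text; none has the unit directly after a converted sign and number, so they are a weak test of this kind of failure. The SAP is a separate file and says little about how the protocol page was read. All of this stands, and it is why the point is conditional.

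A second objection is that Protocol 8.4 already supplies the unit, so a sensible site would read the threshold in pg/mL. That is probably how it would be handled, but it leaves a mandatory criterion to be applied otherwise than as printed.

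A third concerns consequences. A reader might infer that no subject could qualify, or that every enrolled subject deviates from the criterion. The documents do not support either inference: they give no ACTH reference range, no expected ACTH level in CAH and no assay limits, so neither can be shown from the plan. Nor does a unit error carry through to the analysis. The safety and pharmacodynamic sets in SAP 6.2.1 depend on dosing and available data, not on eligibility, and no per-protocol set is defined. The sample size is "based on practical clinical considerations with no formal statistical power calculations".

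**Conclusion.** Criterion 6 is wrong as written, conditional on confirmation in the source PDF. As supplied, a mandatory entry threshold is stated in a unit 1,000,000 times larger than the one in which its result is reported.

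The conclusion rests on two conditions: that the extracted μ is what the source prints, and that the central laboratory reports screening ACTH in pg/mL, as Protocol 8.4 indicates. If the source reads pg/mL, the point falls. The conclusion does not extend to how many subjects would meet the criterion, and it does not say what the threshold should be. This is a unit inconsistency in a decision rule; it leaves the planned analyses unchanged.

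**What to change.** 1. Check criterion 6 in the source PDF. If it reads pg/mL, nothing more is needed.
2. If it reads μg/mL, reconcile criterion 6 with the unit that the central laboratory reports and that Protocol 8.4, Protocol 12.7 and SAP 4.3 use. The sponsor should confirm the intended numeric threshold in that unit; the number should not be carried over by assumption.
3. Use the same wording and unit in the eligibility eCRF.
4. State in the CSR which unit and number sites actually applied, so that the deviation review under SAP 8.2 has a fixed reference.

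The first step costs minutes. The second is an administrative correction of one unit, handled as an amendment under Protocol 13.3. If enrolment is already complete, the CSR statement does most of the work. No SAP analysis, table or sample size has to change.
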